1.0 Objectives

1.1 Study Objectives

Often comorbid with obesity, nonalcoholic fatty liver disease (NAFLD) is the leading cause of chronic liver disease in the United States affecting 75-100 million adults, of which 15-20 million have the more severe variant nonalcoholic steatohepatitis (NASH).(1-3) Conservative estimates project a doubling in NASH by 2025.(4-6) The most advanced forms of NAFLD are associated with increased liver-related mortality and lower overall survival. The most effective treatment for NAFLD remains adopting healthy dietary and exercise patterns,(7-14) however NAFLD patients are among the least physically active individuals.(15) Predicting exercise behavior on an individual level is highly complex due to differing motivation, physiologic response to and subjective experience of exercise as well as emerging genetic evidence.(16, 17) The human genome and regulation of gene expression is influenced by physical activity. Patatin like phospholipase-3 (PNPLA3) rs738409 polymorphism (GG, GC and CC genotypes) plays a crucial role in the development of NAFLD.(18-24) The GG genotype is both associated with advanced NAFLD,(18, 25-27) and predicts response to physical activity.(10, 28) Patients with NASH have extensive extrahepatic disease(29) and are hypercoagulable.(30-42) NASH is a prothrombotic state with fibrinolytic dysfunction through elevated plasminogen activator inhibitor (PAI-1), an independent risk factor for venous thromboembolism (VTE). Consequently, patients with NASH are predisposed to VTE;(30-32) the risk of portal vein thrombosis (PVT) in NASH is 210% greater than in other liver disease.(30, 31) NASH patients are also at increased risk for pulmonary embolism (PE) and deep vein thrombosis (DVT). The most advanced forms of NASH have the greatest thrombotic risk. While studies observe that change in diet, weight and physical activity patterns improve NASH, it is not clear whether these lifestyle changes also reduce the elevated clot risk, however, moderate-intensity exercise leads to improved fibrinolysis in healthy persons.

Developing an effective treatment modality to lessen thrombotic risk is imperative for this highly prevalent condition. In this proposal, we seek to begin a line of work to answer the question “Can lifestyle changes effectively mitigate the increased risk of VTE in patients with NASH?” focusing initially on the at-risk population genetically susceptible to advanced disease. We hypothesize that fibrinolysis as measured by PAI-1 will be improved with exercise in patients with NASH. We expect this effect to be determined by changes in body composition as PAI-1 levels are dependent on adiposity.

1.2 Primary Study Endpoints

The primary outcome of interest is change in fibrinolysis as measured by PAI-1 level immediately following completion of the exercise and nutritional counseling program.

1.3 Secondary Study Endpoints

Secondary Outcomes are as follows: (1) Change in PAI-1 after 16-week exercise regimen; (2) Change in other markers of hemostasis [von Willebrand Factor (vWF), P-selection, Protein S, Protein C, Factor VII, Factor VIII, Fibrinogen, Antithrombin,] after 16-week exercise regimen; (3) Change in PAI-1 stratified by PNPLA3 genotype after 16-week exercise regimen; (4) Correlation between loss of hepatic fat as measured by magnetic resonance imaging proton density fat fractionation (MRI-PDFF) and changes in hemostatic markers after 16-week exercise regimen; (5) Correlation between maximal oxygen consumption (VO₂ max) and hemostatic markers after 16-weeks of exercise; (6) health-related quality of life (HRQOL) change following exercise intervention

2.0 Background

2.1 Scientific Background and Gaps

Significance: NAFLD is the leading cause of chronic liver disease in the United States (US). The epidemic of metabolic disease has reached substantial portions with widespread public health impact. Nearly 70% of US adults are overweight or obese. NAFLD is a spectrum of chronic liver disease that is often comorbid with obesity. NASH is the more severe variant of NAFLD, characterized by inflammation and/or fibrosis. NAFLD is the leading cause of chronic liver disease in the US affecting 75-100 million adults (~40% of the adult population); 15-20 million adults have NASH.(1-3) NAFLD rates are projected to double by 2025; conservative estimates suggest 30 million individuals will have been diagnosed with or progressed to NASH.(4-6)

The most advanced forms of NASH are associated with increased liver-related mortality and lower overall survival. NASH is staged based on the degree of fibrosis and ranges from stage 0 (no fibrosis) to stage 4 (cirrhosis). Patients with simple steatosis (no fibrosis) have a favorable prognosis with a 1-2% risk of developing cirrhosis over the subsequent 15-20 years.(43, 44) The risk of progression with NASH (presence of fibrosis) is much greater with cirrhosis rates of 12% over the eight years following diagnosis.(43, 44) NASH with significant fibrosis (stage ≥ 2) is associated with increased liver-related mortality and lower overall survival rates due to cardiovascular events and malignancy.(4-6)

The current standard of care for NAFLD is lifestyle changes through diet and exercise. The American College of Sports Medicine (ACSM) recommends all persons participate in ≥ 30 minutes of moderate-intensity physical activity 3-5 times/week and to perform strength training two times/week.(45) The mainstay of NASH treatment is lifestyle change through adopting healthy diet and exercise routines,(7-14) an effect that may be independent of weight loss.(46, 47) A recent meta-analysis by Katsagoni *et al.*(48) comprised of twenty high-quality randomized controlled trials (RCTs) (n=1,043) found a favorable pooled effect of exercise (improved liver associated enzymes and intrahepatic fat), independent of dietary counseling, however, it is unknown if exercise improves fibrosis. The authors found no discernable difference between aerobic exercise and strength training, however, intensity of training was associated with different results and moderate-to-high volume intensity resulted in better response.(48) Sustainable exercise remains challenging in clinical practice owing to factors that are often outside the control of the treating physician. NASH patients are among the least physically active individuals.(15, 49) Only 20% of patients with NASH achieve the recommended daily physical activity amount and intensity. NASH patients have greater ratings of perceived exertion at similar exercise thresholds,(50) lower physical function and lower performance status.(49, 51) A sedentary lifestyle promotes NASH progression; lower levels of activity are associated with greater intrahepatic fat and inflammation.(52, 53)

The human genome and regulation of gene expression is influenced by physical activity. Over time, humans have become increasingly sedentary and as a consequence, our current genome has become maladapted resulting in abnormal gene expression and manifestation of chronic disease, including NASH.(54) Genes that were once favorable during times of starvation have now become overexpressed and pathologic resulting in metabolic dysfunction and sarcopenia.(54) Restoration of this perturbed metabolic homeostasis can be accomplished through habitual exercise in our sedentary culture.(54) To date, the expression of thirty plus genes important to chronic inflammation have been found to be regulated by exercise.(55) The PNPLA3 rs738409 polymorphism (a missense variant resulting in cytosine to guanosine substitution which encodes for an isoleucine to methionine substitution at amino acid position 148) leads to abnormal protein production and subsequent accumulation of triglycerides in the liver, independent of obesity.(18-21) PNPLA3 plays a crucial role in NASH development and progression to cirrhosis via interaction with behavioral risk factors including physical inactivity.(22-24, 56) And while PNPLA3 activity is modulated by hyperinsulinemia and carbohydrate deficiency, the effect of exercise on PNPLA3 gene expression is unknown.

PNPLA3 genotype is associated with advanced NASH and predicts response to physical activity. The PNPLA3 GG genotype is associated with the most advanced forms of NASH.(18, 25-27) PNPLA3 predicts

response to lifestyle intervention(10, 28) with the greatest benefit being derived by GG homozygotes.(28) In their RCT of 154 subjects, Shen *et al.* (10) found GG homozygotes had the greatest decrease in body weight, body mass index (BMI) and intrahepatic triglyceride (IHTG) even when adjusting for higher baseline IHTG percentages. Additionally, compound GC heterozygotes were more likely than CC homozygotes to experience weight loss, decrease in BMI and reduction in IHTG. In fact, for each G allele, a nearly 3% more absolute reduction in IHTG was observed with exercise intervention. G-allele substitution occurs 40-45% in NAFLD.(19)

NASH is a prothrombotic state with fibrinolytic dysfunction through elevated PAI-1.

Chronic inflammation from hepatic steatosis(34-37) culminates in activation of the coagulation system and abnormalities in all three phases of hemostasis. (38, 39) Hemostasis can be broken down into primary, secondary and tertiary components.(57) Increased platelet activation (primary hemostasis) has been observed in NASH as have elevated levels of vWF.(39, 40, 58) Hypercoagulability (secondary hemostasis) in NASH manifests through increased levels of Factor VIII and fibrinogen.(38, 39) Levels of anticoagulants antithrombin and protein C are decreased in NASH, tipping the hemostatic balance towards clotting. The most severe prothrombotic imbalance is seen in parallel with the most advanced disease (including NASH cirrhosis).(38, 39)

PAI-1 is elevated in NASH while tissue activating factor antigen and tPA are decreased. This leads to a chronic state of hypofibrinolysis (tertiary hemostasis). (39) Similar to the Factor VIII-to-Protein C ratio, PAI-1 correlates histologically with increasing severity of steatohepatitis and fibrosis.(41) Additionally, patients with NASH have longer clot lysis times and greater clot density.(58) Elevated PAI-1 promotes thrombotic risk and may accelerate liver disease progression due to local tissue ischemia stemming from intrahepatic thrombi, known as *parenchymal extinction*.(59) Clinically, the presence of at least one thrombotic risk factor is associated with a nearly two-fold fibrosis stage increase in NASH, further supporting the notion of thrombosis and disease progression.(42, 60)

Patients with NASH are predisposed to VTE. The hemostatic environment in patients with chronic liver disease is a precarious balance between pro- and anti-thrombotic factors. Patients with NASH cirrhosis are at increased risk for thrombosis. Independent of metabolic comorbidities, liver transplant recipients with NASH have a 55% greater risk of PVT. The odds of PVT increase exponentially for high-risk NASH (age >60 years with diabetes, hypertension and obesity) [OR 2.1 (95% CI 1.6-2.8)].(30-32, 61) Our preliminary data [accepted, 2017 American Association for the Study of Liver Diseases (AASLD) Liver Meeting] documents further coagulation derangement in NASH. We found the thrombotic state extends from the portal venous to the systemic circulation as the risk of VTE (PE/DVT) was two and a half-fold greater in hospitalized patients with NASH cirrhosis, supporting work by Di Mino *et al.*(33)

PAI-1 modulates fibrinolysis and is an independent risk factor for VTE. Decreased fibrinolytic activity is a risk factor for VTE.(62, 63) PAI-1, which is produced by adipose tissue and consequently elevated in obesity and NASH and reduced by weight loss,(64) inhibits breakdown of fibrin based clots through physiologic inhibition of plasminogen activators (e.g. urokinase). Elevated PAI-1 levels lead to longer clot lysis times.(65) Multiple studies have documented PAI-1 to be an independent predictor of PE, DVT and PVT when adjusting extensively for prothrombotic confounders.(65-67) PAI-1 is one of the stronger independent risk factors for PVT [OR 6.4 (95% CI 2.5-16.1)].(66) The 4G/5G PAI-1 polymorphism confers additional risk for VTE.

Moderate-intensity exercise leads to improved fibrinolysis in healthy persons. Exercise has a favorable effect on the coagulation system across all three phases of hemostasis.(68-70) Habitual exercise improves primary hemostasis via endothelial-dependent vasodilation and nitric oxide production leading to less platelet activation and aggregation.(71) Moderate intensity exercise improves hemostasis efficiency by activating fibrinolysis in concert with improving coagulation.(68, 69) Specifically, chronic aerobic based training leads to improved fibrinolytic activity in both healthy subjects and those with

cardiovascular disease. This occurs during exercise and persists at rest.(68, 69, 72-75) Reductions in PAI-1 following aerobic exercise programs lasting 3-8 months range from 23-37%.(72, 74-76) When comparing subjects who are aerobically trained to those who are not, further benefit has been observed in fibrinolytic activity via skeletal muscle tPA efficiency.(73) Patients with higher baseline PAI-1 experience the greatest benefit from exercise through both weight and fat loss.(72, 75, 77)

As the obesity epidemic continues to worsen, prevalence rates of NASH are increasing and threaten to overwhelm the healthcare system. The most effective treatment for NASH remains exercise however, predicting which patients will achieve a response to exercise remains more of an art than a science. Genetics may play a role with this response and can be used to identify the patients most likely to derive benefit. NASH patients have significant extrahepatic disease including thrombotic events. Despite the longstanding knowledge that inflammation leads to thrombosis, exercise improves NASH (a thrombotic state), and chronic aerobic exercise improves fibrinolysis through PAI-1 (independent risk factor for VTE), the effect of exercise on thrombosis in this at-risk population remains unknown. We hypothesize that increased physical activity will decrease hepatic fat and adipose tissue leading to less PAI-1 associated thrombotic risk.

2.2 Previous Data

(1) Definition of clinically important thrombotic events in patients with NASH. [name] published two large cross-sectional studies documenting the increased risk of PVT in NASH.(30, 31) Of the 33,368 subjects who underwent liver transplantation between 2003-2012, 6.3% (n=2,096) had PVT. 12% of recipients with NASH had PVT compared to 7% in all other etiologies of liver disease (p<0.001), a finding that remained statistically significant when adjusting for metabolic confounders. Additionally, liver transplant recipients with high-risk NASH have even greater risk for PVT at the time of liver transplantation with prevalence rates of 14%.

(2) Feasibility of administration of Patient Reported Outcomes Measurement Information System Computerized Adaptive Testing (PROMIS-CAT) to patients with chronic liver disease. [name] completed a pilot study of 109 adult liver transplant candidates enrolled over three months. Through iPad platform, subjects completed the PROMIS-CAT. All subjects completed the PROMIS-CAT (100% conversion) and average completion times were ~15 minutes. The results of this pilot are helpful in that this novel, technologically advanced model is readily completed by subjects with advanced medical illness.

22% of patients with NASH cirrhosis, whereas

(3) Development of an exercise training model. [name] developed and led a 16-week aerobic exercise program training both sedentary and moderately active adults to increase their cardiopulmonary fitness culminating in competition in an amateur sprint triathlon. [name] was previously a certified indoor cycling instructor, team captain and varsity collegiate lightweight rower at Penn State and an elite amateur triathlete. He has a Bachelor's of Science Degree from Penn State in Nutritional Sciences, awarded with honors in 2005.

(4) Previous principal investigator of a small clinical trial. Under the mentorship of [name] (collaborator), [name] studied twelve patients in a RCT enrolling hospitalized subjects with decompensated cirrhosis and hepatorenal syndrome. [name] served as principal investigator (PI) and administrative contact for the study for two years. The manuscript was recently accepted and published in *Annals of Hepatology*. During this experience, [name] obtained the skillset necessary to be an effective PI for clinical trials.

2.3 Study Rationale

Despite the longstanding knowledge that inflammation leads to thrombosis, exercise improves NASH (*a thrombotic state*), and chronic aerobic exercise improves fibrinolysis through PAI-1 (*independent risk*

factor for VTE), the effect of exercise on thrombosis in this at-risk population remains unknown. Similarly, while exercise is known to influence pro-inflammatory gene expression, modulation of PNPLA3 activity through exercise is unknown.

3.0 Inclusion and Exclusion Criteria

3.1 Inclusion Criteria

- Adults age ≥ 18 or < 70 years
- Liver biopsy ≤ 6 months prior to enrollment
- Biopsy proven NASH(78)
- Lack of secondary causes of hepatic fat accumulation:
 - Significant alcohol consumption (< 21 drinks/week for men and < 14 drinks/week for women)
 - Chronic hepatitis C
 - Wilson disease
 - Lipodystrophy
 - Parenteral nutrition
 - Long-term use of steatogenic medications (mipomersen, lomitapide, amiodarone, methotrexate, tamoxifen, corticosteroids)
 - Monogenic hereditary disorders

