3.2 Exclusion Criteria

- > 90 minutes/week of at least moderate intensity exercise over the previous three months as assessed by the Get Active Questionnaire (GAQ).
- Pregnancy
- BMI < 18 or > 45 kg/m²(16)
- Uncontrolled diabetes (changes in medication dosing over the previous three months or hemoglobin A1c $> 9\%$)(12)
- Active cardiac symptoms
- Severe medical comorbidities/psychiatric illness
- Decompensated cirrhosis (history of esophageal varices, ascites or hepatic encephalopathy)
- Cancer with life expectancy < 6 months
- MRI contraindications (severe claustrophobia, implanted ferrous metal)
- Other liver disease (positive hepatitis B surface antigen)
- Active weight-loss program participation or weight-loss supplement use
- Active substance abuse/smoking
- Inability to provide informed consent
- Institutionalized/prisoner
- Inability to walk > 2 blocks or $\frac{1}{4}$ mile
- Concurrent use of antiplatelet medications excluding aspirin 81 mg once daily as aspirin
- Non-English-speaking patients due to unavailability of translators for all visits/sessions

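### Two inclusion rules in section 3.1 do not say what they appear to intend: the alcohol item labels intake below the limit as significant, and the upper age bound has no effect

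*Combined protocol and SAP*

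**What the plan says.** Both lines are in section 3.1, Inclusion Criteria, of the combined protocol and SAP.

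- **Age:** "Adults age ≥ 18 or < 70 years".
- **Alcohol:** the parent criterion is "Lack of secondary causes of hepatic fat accumulation", and the first item beneath it is "Significant alcohol consumption (< 21 drinks/week for men and < 14 drinks/week for women". The six other items are chronic hepatitis C, Wilson disease, lipodystrophy, parenteral nutrition, long-term steatogenic drugs and monogenic hereditary disorders. Each is something the subject must not have.

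Section 3.2, Exclusion Criteria, has no age limit and no drink limit. Its nearest item is "Active substance abuse/smoking", which carries no threshold. Section 4.4, on eligibility and screening, is marked not applicable. Section 4.1 places the phone-screen procedure in an attachment that is not part of the document reviewed.

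**The concern.** These are operative thresholds. Section 4.1 has portal emails going to patients who meet the basic criteria, so someone has to turn the criteria into a filter. Section 10.1 requires that eligibility be confirmed before enrolment, and section 20.1 opens the records to audit. A rule used in these ways should give the right answer when followed exactly, and neither line does.

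The alcohol item helps establish that the liver disease is non-alcoholic, which defines the trial population. As worded, it points the wrong way. The age line appears to set an upper limit but sets none, so enrolling someone aged 70 or over would comply with the text and need not be recorded as a deviation.

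**Working it through.** The plan gives no figure to reproduce here. The check is one of logic, by enumeration.

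**Age line (section 3.1)**

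- Rule as written: admit if age ≥ 18 or age < 70.
- To fail it, a person would have to be both under 18 and at least 70, which is impossible. The rule is therefore true at every age.
- Over integer ages 0 to 120, it admits 121 of 121. Over adult ages 18 to 120, it admits 103 of 103. The only working restriction is the word 'Adults'.
- For comparison, with 'and' the rule admits ages 18 to 69, that is 69 − 18 + 1 = 52 of the 103 adult ages. The difference, 103 − 52 = 51, is ages 70 to 120. These are counts of ages on a grid, not of subjects.
- The body mass index line in section 3.2 also joins two bounds with 'or' (below 18, above 45). That is correct in an exclusion rule, where failing either bound excludes. In an inclusion rule, the same word removes the limit.

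**Alcohol item (section 3.1)**

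- Parent rule: the listed item must be absent.
- Item as defined: significant intake means fewer than 21 drinks a week (men) or fewer than 14 (women).
- Literal criterion: pass if not (drinks < 21) for men, or not (drinks < 14) for women.

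| Sex | Counted as significant, so fails the item | Passes the item | At 0 drinks a week |
|---|---|---|---|
| Men | 0 to 20 | 21 or more | fails |
| Women | 0 to 13 | 14 or more | fails |

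**Does anything else repair the lines?** Section 3.2 gives neither an age range nor a drink limit, section 4.4 is empty, and no other section restates either threshold.

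**Could text extraction explain it?** A fault in the alcohol signs cannot be wholly ruled out. However, the other inequality signs in sections 3.1 and 3.2 read sensibly, and the fault in the age line is a word, not a symbol.

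**The case against.** The strongest reply is that nobody would apply these lines literally. The disease is non-alcoholic by name, biopsy-proven NASH is required, and the list is about causes to be ruled out. A reading that admits only heavier drinkers is absurd, so the bracket is naturally taken as the permitted intake. Likewise, a stated bound of 70 has no purpose unless it is an upper limit. The study PI conducts the initial consultation and consent (sections 5.1.1.1 and 7.2), and the unseen phone-screen attachment may word the rules correctly. All of this stands. It limits the practical harm and sets the severity, but it does not make the text correct.

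A reader might also infer three stronger conclusions, which the documents do not support:

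- **That the alcohol item reverses eligibility for every subject.** It does not. It is one of many criteria that must all be met. A person who fails on biopsy timing, body mass index or activity level is ineligible under either reading, and a heavier drinker who passes this item may still be caught by "Active substance abuse/smoking", although that item has no threshold and does not repair the line.
- **That every properly enrolled subject would deviate from the text.** For the age line this is false, since ages 18 to 69 satisfy it with either connective. Such an argument could be made only for the alcohol item.
- **That the missing age limit is a safety failure because subjects undergo maximal exercise testing.** The documents give no safety reason for the bound of 70. Exercise risk has its own controls: the cardiac, comorbidity and walking exclusions in section 3.2, and the baseline ECG and supervised VO2 max testing in section 7.2.

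**Conclusion.** Both wording faults are present on the face of section 3.1, and nothing elsewhere in the document corrects them. The age line excludes no adult. The alcohol item, taken with its parent criterion, fails abstainers and passes men at 21 or more and women at 14 or more drinks a week on that one criterion.

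The severity is low. The conclusion rests on two assumptions: that the extracted inequality signs match the source, and that the bracket defines the item it follows, as the structure of the list implies. How many subjects are affected cannot be estimated from the documents, and there is no evidence that either rule was misapplied. Sample size, power and the primary analysis are not in question.

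**What to change.** Amend section 3.1 in two places.

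1. Reword the alcohol item so that its inequality agrees with the parent criterion, which requires absence. The investigators should confirm the limits they intend, including which side of the line exactly 21 or 14 drinks falls on. No new threshold is proposed here.
2. Join the two age bounds with 'and' if both are meant to apply. If no upper limit is intended, delete the second bound.

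Check the phone-screen attachment and any portal email filter against the amended wording. The cost is two small text edits by amendment, with no change to design, sample size or data collection.
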